4.7.3. Subgroup analyses for efficacy endpoints

Analyses described in 4.7.1 and 4.7.2 will be performed in subgroups defined in 3.2 (with sex dropped from model specification when analyzing males and females independently).

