2.3. Study design

This is a double-blind, randomized, placebo controlled, parallel group, dose ranging study to explore the efficacy, safety, tolerability, and PK parameters of two different doses of CPL500036 (PDE10A inhibitor) in patients with an acute exacerbation of schizophrenia when administered for 28 days.

The study will be conducted at multiple clinical units. Approximately 165 patients will be randomized at a 1:1:1 ratio to receive 20 mg CPL500036, 40 mg CPL500036 or placebo.

The study will comprise of a Screening Period (that will include a prior Medication Washout Period), a Treatment Period and a Follow-up Period.

For the Screening Period, patients will undergo screening assessments from Day -10 to Day -8 in multiple settings (i.e., emergency departments, outpatient clinics, etc.). Rolling admission will be employed in this study. Patients that fulfil all the inclusion criteria and none of the exclusion criteria will immediately be admitted to the Clinical Unit and enter a Medication Washout Period of up to 7 days (Day -7 to Day -1) before the start of the 28-day Treatment Period. The duration of the Medication Washout Period may be shorter or omitted for non-medicated patients.

During the Treatment Period, patients will be dosed with 20 mg CPL500036, 40 mg CPL500036 or placebo once daily for 28 consecutive days (Day 1 to Day 28). Patients will remain in-house for the duration of the Treatment Period.

Approximately 30% of the patients (17 patients in each of the 3 treatment groups) will undergo extensive PK sampling during the Treatment Period, and the remaining 70% of the patients will only undergo sparse PK sampling.

On Day 29, the patients may resume anti-psychotics treatment. The Investigator will continue to monitor the patient for safety and clinical stability. Patients will be discharged from the Clinical Unit based on local standards of care if the patient is in a stable condition under the regular medication(s).

After discharge from the Clinical Unit, patients will return to the Clinical Unit for 2 once weekly Follow-up Visits, $7 (\pm 1)$ and $14 (\pm 1)$ days after the last dose of the investigational medicinal product (IMP) (Day 35 and Day 42).

Patients that withdraw or are withdrawn from the study will attend an early termination visit at the Clinical Unit and 2 safety Follow-up Visits 7 (\pm 1) and 14 (\pm 1) days after the last dose of IMP.

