2.4. Sample size

This proof-of-concept study is powered to rule out an effect size of 0.5 or greater for the primary endpoint. With 50 patients per group, the study has 80% power to detect an effect size of 0.5 or greater for 1 of the 2 dose groups, compared to placebo, given a 2-sample t-test, and a 2-sided 10% significance level. Each dose will be compared to placebo, without adjustment for multiplicity so the type-I error will be slightly inflated, however, as this is a proof-of-concept study, the slight inflation is acceptable. Assuming an approximately 10% of patients may drop out, approximately 165 patients will be randomized (55 patients per group).

3. General aspects of the statistical analysis

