3.2. Definition of subgroups

Analysis of primary and secondary endpoints will be provided for FAS and PP population by the following subgroups:

- Sex (male, female).
- Baseline (Day -1) PANSS (low <95, high ≥95).

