4.1. General

Due to exploratory nature of the study statistical significance level will be equal to 0.1. Based on provided assumption on the effect size this study is not sufficiently powered to reject the null hypothesis for the primary study endpoint at the more conventional significance level of 0.05. P-values ≥0.001 will be reported to 3 decimal places; p-values less than 0.001 will be reported as "<0.001". The mean, standard deviation, and any statistics other than quantiles, will be reported to one decimal place greater than the original data. Quantiles, such as median, or minimum and maximum will use the same number of decimal places as the original data. Estimated parameters, not on the same scale as raw observations (e.g. regression coefficients) will be reported to 3 significant figures.

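### Subgroup efficacy analyses are separate fits with their own p-values and no treatment-by-subgroup test; at the design effect with an assumed even split, exactly one of the two subgroups is significant about half the time

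*SAP*

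**What the plan says.** SAP 3.2 defines two factors, sex and Day -1 PANSS total with a cut at 95, and sets the scope: "Analysis of primary and secondary endpoints will be provided for FAS and PP population by the following subgroups". SAP 4.7.3 gives the method: "Analyses described in 4.7.1 and 4.7.2 will be performed in subgroups defined in 3.2". It adds that men and women are modelled independently, with sex removed from the model.

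The analyses carried into each subgroup produce tests:

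- SAP 4.7.1 gives LS means, 90% CIs and p-values for each dose against placebo.
- SAP 4.7.2 gives, for the responder endpoints, a p-value against placebo from a proportion test at the two-sided 10% level, plus a logistic model.

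The level comes from SAP 4.1: "statistical significance level will be equal to 0.1". The 4.7.1 model contains treatment, timepoint, their interaction, site and baseline score. Its only interaction is treatment by timepoint. Neither document contains a treatment-by-subgroup term, a heterogeneity test or a rule for reading subgroup p-values. Protocol section 10 does not describe these subgroup analyses.

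**The concern.** Whether the treatment effect differs between two subgroups is a question about the difference between two estimates. Two separate p-values against placebo do not answer it. When each subgroup has only moderate power, one p-value below 0.10 beside another above it is an ordinary result even if the effect is identical in both. The SAP will produce such pairs for each dose and each factor, and it plans no statistic that separates chance discordance from real heterogeneity. What is at stake is how the subgroup tables are read. The primary comparison is not affected.

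**Working it through.** **Inputs**

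- Effect size 0.5, 50 per group, 80% power (SAP 2.4): "With 50 patients per group, the study has 80% power to detect an effect size of 0.5 or greater".
- Test and level (SAP 2.4): "given a 2-sample t-test, and a 2-sided 10% significance level".
- Allocation (SAP 2.3): "Approximately 165 patients will be randomized at a 1:1:1 ratio".
- Subgroup split: not in the documents. Assumed 50/50 as the base case, with a range to 80/20 and the same split in each arm.

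**1. The plan's own figure.** Two-sample t-test, noncentral t, n = 50 per arm, d = 0.5, two-sided 10%: power = 0.799. The stated 80% is reproduced.

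**2. Power within a subgroup.** A 50/50 split leaves 25 per arm. The same formula gives power 0.539.

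**3. Chance that exactly one subgroup is significant.** The two levels of a factor contain different patients, so the tests are independent:

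P(discordant) = p1(1 − p2) + p2(1 − p1)

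For 50/50 this is 2 × 0.539 × 0.461 = 0.497. A simulation gives 0.49–0.50.

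| Split of 50 per arm | Power, larger subgroup | Power, smaller subgroup | P(discordant) |
|---|---|---|---|
| 25/25 | 0.539 | 0.539 | 0.50 |
| 30/20 | 0.606 | 0.464 | 0.51 |
| 35/15 | 0.665 | 0.380 | 0.54 |
| 40/10 | 0.716 | 0.288 | 0.59 |

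**4. Dependence on the true effect** (50/50 split, same effect in both subgroups):

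| True effect (SD) | 0 | 0.3 | 0.4 | 0.5 | 0.6 | 0.7 | 0.8 |
|---|---|---|---|---|---|---|---|
| P(discordant) | 0.18 | 0.40 | 0.48 | 0.50 | 0.44 | 0.34 | 0.22 |

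**5. Opposite directions are rare.** Each subgroup difference has SE √(2/25) = 0.283. At a true effect of 0.5, the chance that one estimate is negative is Φ(−0.5/0.283) = 0.039. Exactly one of the two is negative with probability 2 × 0.039 × 0.961 = 0.07.

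**6. Effect of baseline adjustment.** The documents give no baseline–outcome correlation. If it were 0.5, the effect in residual SD units would be 0.5/√(1 − 0.25) = 0.577, power per subgroup 0.643, and discordance 2 × 0.643 × 0.357 = 0.46. At a correlation of 0.6 the effect is 0.625, power 0.703 and discordance 0.42.

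**7. What an interaction test does instead.** The difference between two subgroup effects has SE √(2/25 + 2/25) = 0.40 SD.

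- False-positive rate when the effect is common: 10% by construction per dose and factor (simulated 9.8%).
- At least one false positive across four tests (2 doses × 2 factors): 0.32 simulated, with shared placebo and even splits. If the tests were independent it would be 1 − 0.9⁴ = 0.34.
- Power for a 0.5 SD difference in effect: Φ(0.5/0.40 − 1.645) = Φ(−0.395) = 0.35.
- Power for a 1.0 SD difference: Φ(1.0/0.40 − 1.645) = Φ(0.855) = 0.80.

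**The case against.** This is a proof-of-concept study that states openly that it does not adjust for multiplicity. It plans no subgroup hypothesis, enrichment rule or claim of a differential effect. The 90% CIs will stand beside the p-values, so a careful reader will see them overlap. An interaction test is weak at this sample size, and four of them still give about a one-in-three chance of some false positive.

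Much of that stands, and it is why this is an inexpensive improvement and not a flaw in the main analysis. It does not close the gap. SAP 4.1 uses the exploratory nature of the study to justify the 10% level; it does not limit subgroup results to description. Overlap of two intervals is also an imprecise substitute for an interval on the difference.

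A reader might infer several stronger things that the documents do not support:

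- **That subgroups will point in opposite directions half the time.** Discordance here means one p-value below 0.10 and one not. Opposite signs occur about 7% of the time at 0.5 SD.
- **That one half is a general rate.** It holds near 0.4–0.6 SD, per dose and per factor.
- **That a chance subgroup result will decide the next trial's population.** Nothing in either document says so.
- **That the subgroup fits will fail to converge, or that site groups will shrink below five.** The SAP provides fallback covariance structures, and it does not say whether its five-patient pooling minimum is applied before or within subgroups. Neither outcome can be shown.

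**Conclusion.** The point holds as a minor one. The SAP plans within-subgroup p-values and no test of whether the effect differs between subgroups. At its own design effect and level, a common effect produces one significant and one non-significant subgroup about 50% of the time per dose and factor. A 10% interaction test would wrongly signal a difference 10% of the time.

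The 50% rests on 50 evaluable patients per arm, an assumed even split, a true effect of 0.5 SD in both subgroups, and an unadjusted t-test. Uneven splits up to 80/20 raise it to 59%. With an even split, effects well away from 0.5 SD lower it, to 18% at zero and 22% at 0.8 SD. Baseline adjustment would change it somewhat. The primary analysis and sample size are untouched.

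**What to change.** For the primary endpoint, fit one FAS MMRM per subgroup factor. Add to the 4.7.1 model: subgroup, subgroup-by-timepoint, treatment-by-subgroup and treatment-by-subgroup-by-timepoint. From that model report:

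- the Week 4 treatment-by-subgroup contrast for each dose, with its 90% CI and p-value;
- the LS-mean difference from placebo in each subgroup for each dose, with 90% CIs.

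State in SAP 4.7.3 that all subgroup results are descriptive and that within-subgroup p-values are not evidence of a differential effect. State the limits as well: about 35% power for a 0.5 SD difference in effect and 80% for 1.0 SD (50 per arm, even split), and about a 32% chance of at least one false positive across the four interaction tests at 10%.

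Separately, correct the 4.7.3 wording on sex. The 4.7.1 model has no sex term to drop, so either the wording or the model specification is wrong.

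The cost is a paragraph of SAP text and one extra model for each of the two factors. No data collection changes.

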4.8. Safety analyses

Safety data will be summarized for the safety population (SS).

4.8.1. Adverse event analysis

Any undesirable signs, symptoms or medical conditions occurring or worsening of pre-existing conditions between signing informed consent and the first administration of the study medication are considered as pre-treatment AEs. Undesirable signs, symptoms or medical conditions or worsening of pre-existing conditions occurring after the first administration of study medication are considered as treatment emergent adverse events (TEAEs).

A TEAE will be analyzed as related to study medication (i.e. as adverse drug reaction, ADR) if the relationship to study treatment was documented as 'unlikely', 'possible', 'probable', or 'definite' or if the relationship to study treatment is missing.

An overview table presenting the incidence of the following AE categories will be presented. Percentage of patients in each category will be compared between treatments as a difference in proportions between treatments including a 95% CI based on the Agresti – Caffo method (2000):

- All AEs
- Pre-treatment AEs
- Serious AEs (SAEs) (including pre-treatment SAEs)
- Treatment emergent AEs (TEAEs)
- Treatment emergent SAEs (TESAEs)
- Severe TEAEs
- Related TEAEs
- Related severe TEAEs
- TEAEs leading to reduction of dose
- TEAEs leading to interruption of dose
- TEAEs leading to permanent discontinuation (i.e. withdrawal) of study medication
- Related TEAEs leading to permanent discontinuation of study medication
- AEs leading to death (i.e. outcome of AE is fatal)
- TEAEs leading to death
- Related TEAEs leading to death

All treatment emergent AEs (TEAEs) and all serious TEAEs will be tabulated by MedDRA SOC and PT presenting the number and percentage of patients reporting the AE and the number of AEs reported. Additional tables will distinguish the events by whether the AE was related to study medication and by maximum severity.

All AEs documented in the eCRF will be listed by patient. Data listings will include patient ID, treatment group, verbatim term, preferred term, system organ class, start and stop date and relative day of the AE, severity, medications (yes/no), seriousness, action taken with study medication, relationship to study medication, and outcome will be provided. TEAEs will be flagged as such. In addition, separate listings for all SAE's, deaths and AEs leading to discontinuation (action taken with study treatment = drug withdrawn, or AE is reason for early termination) will be presented.

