5. STUDY POPULATION

The study population will consist of male and female patients with an acute exacerbation of schizophrenia. Subjects must be able to provide written informed consent and meet all the inclusion criteria and none of the exclusion criteria.

NOTE: Investigators should ensure that all study enrollment criteria have been met at screening and on Day -1. If a patient status after screening changes at baseline (Day -1) such that the study patient no longer meets all eligibility criteria, then the patient should be excluded from participation in the study (such patient is to be considered as screen failure). It should be remembered that all baseline procedures must be performed on Day -1, but final patient qualification should be made when all results are available, before randomization on Day 0.

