5.4.3. Prior and Concomitant Treatments

Medication restrictions applicable before dosing are described in Section 5.3 (exclusion criteria). Prior medication will be recorded.

Any medicinal product, prescribed or over-the-counter (OTC), taken by a subject other than the IMP, is considered concomitant medication. Permitted medication (for prolonged use) includes only paracetamol in recommended doses (≤ 2 g per day) after approval by the Investigator or designee. Higher doses of paracetamol, up to 4 g per day may be given at the discretion of the

Investigator or designee to treat AEs such as fever and headache (only for short terms issues). Any concomitant treatment will be given only if deemed strictly necessary by the Investigator or designee. Use of concomitant medication will be recorded and reported.

Allowed concomitant medications taken by the patient in fasting conditions can be taken consistently with the current recommendations, but at least 1 hour interval between concomitant medication and IMP administration must be maintained with IMP taken as first.

Starting on the first day of Screening Period and as applicable, all antipsychotic or other psychotropic medications will be stopped with clinically appropriate titration down as per Investigator clinical judgment. Thereafter, patients will be instructed not to take any medications during the conduct of the study unless approved by the Investigator. Any patient who is unable to be safely discontinued from current antipsychotic therapy or other psychotropic medications will not be eligible for the study (see Section 7).

Medication history (psychotropic medication history during the previous 5 years and all other medications during the past 12 months) will be recorded at Screening (Visit 1) in the eCRF. Thereafter, any changes in concomitant medications or new medications added will be recorded in the eCRF.

Patients will not be eligible for the study if they have used any depot antipsychotic within 1 month (30 days) prior to Screening. The using of mianserin, mirtazapine, nefazadone, cyproheptadine, or fluvoxamine within 1 month (30 days) before Screening is not recommended.

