8.3. Safety Variables

8.3.1. Adverse Events

Adverse event reporting will begin for each subject from the date the informed consent form (ICF) is signed and will continue until the final Follow-up Visit.

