10.1.3. Analysis population

- Full Analysis Set (FAS): All patients randomized to either CPL500036 or placebo based on planned treatment regimen irrespective of their compliance to the planned course of treatment (intent-to-treat principle).
- Per Protocol (PP) Set: Patients from the FAS who completed the Treatment Period (Day 28) on study treatment without a major protocol deviation. Protocol deviations will be determined prior to unblinding.
- Safety Set (SS): All patients who received at least 1 dose of study treatment (either CPL500036 or placebo).
- Pharmacokinetic Set (PS): All subjects in the safety set with at least 1 evaluable PK parameter.
- Pharmacokinetic Set for parameter calculation (PSPC): All subjects in the safety set with extensive PK sampling that have at least 1 PK parameter evaluable and without any major protocol deviation thought to interfere with the absorption, distribution, metabolism, and excretion of CPL500036.

The FAS will be the primary analysis set used for all efficacy analyses and the PP analysis set will be used for supportive analyses of the primary and secondary efficacy endpoints. Patients will be included in the treatment group they were randomized to. The SS will be used for all safety analyses and patients will be included in the treatment group based on the treatment they actually received.

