3.1. Analysis populations

The following populations are to be analyzed:

- Full Analysis Set (FAS): All patients randomized to either CPL500036 or placebo based on planned treatment regimen irrespective of their compliance to the planned course of treatment (intent-to-treat principle).
- Per Protocol (PP) Set: Patients from the FAS who completed the Treatment Period (Day 28) on study treatment without a major protocol deviation. Protocol deviations will be determined prior to unblinding.
- Safety Analysis Set (SS): All patients who received at least 1 dose of study treatment (either CPL500036 or placebo).
- Pharmacokinetic Set (PS): All patients in the safety set with at least 1 evaluable PK parameter.
- Pharmacokinetic Set for parameter calculation (PSPC): All patients in the safety set with extensive PK sampling that have at least 1 PK parameter evaluable and without any major protocol deviation thought to interfere with the absorption, distribution, metabolism, and excretion of CPL500036.

The FAS will be the primary analysis set used for all efficacy analyses and the PP analysis set will be used for supportive analyses of the primary and secondary efficacy endpoints. Patients will be included in the treatment group they were randomized to. The SS will be used for all safety analyses and patients will be included in the treatment group based on the treatment they actually received.

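### Pre-treatment AEs and SAEs are tabulated only in dosed patients, so events that led to exclusion during washout appear only in listings; the same table puts between-arm intervals on rows that contain pre-treatment events

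*SAP*

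**What the plan says.** Collection starts early. Protocol 8.3.1 states: "Adverse event reporting will begin for each subject from the date the informed consent form (ICF) is signed". Protocol 8.3.1.1.1 adds that untoward events in treatment-free periods, screening included, are recorded as AEs.

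SAP 4.8.1 classes findings that arise "between signing informed consent and the first administration of the study medication are considered as pre-treatment AEs". Its overview table has a row for pre-treatment AEs, an SAE row that expressly includes pre-treatment SAEs, an all-AE row, and a row for all fatal AEs beside one for fatal treatment-emergent AEs. For every category the arms are compared by a difference in proportions with a 95% Agresti-Caffo interval.

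The population is narrower than the collection window. SAP 4.8 summarises safety data in the SS, which SAP 3.1 defines as "All patients who received at least 1 dose of study treatment". Protocol 10.1.3 agrees: "The SS will be used for all safety analyses".

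Between consent and first dose the protocol changes treatment. Under Protocol 5.4.3, from the first day of screening "all antipsychotic or other psychotropic medications will be stopped with clinically appropriate titration down". Protocol 4.1 allows a washout of up to 7 days before randomization on Day 0, shortened or omitted for unmedicated patients.

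**The concern.** Some patients are removed before dosing because of what happens in washout. If their events are absent from the pre-treatment rows, those rows describe only patients who came through washout fit to be dosed. A reader of the study report could take the percentage as the risk of the withdrawal phase. That risk bears on the argument in Protocol 2.5, which defends placebo control and monotherapy by saying the design minimises risk to participants.

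The arm comparison raises a separate question. Events before the first dose cannot be caused by the assigned treatment. An interval on the pre-treatment row informs nobody, and mixing such events into the all-AE and SAE rows blurs contrasts that could be read as treatment effects.

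**Working it through.** **1. Who is missing from the tables.** The plan gives no figure here, so the check sets the rules side by side.

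- Protocol 5.4.3: a patient who cannot be safely taken off current psychotropic medication is not eligible.
- Protocol 5.3, criterion 10: a positive C-SSRS item 4 or 5 on Day -1, or imminent risk of suicide or injury in the investigator's view, excludes the patient.
- Protocol 5: anyone who no longer meets the criteria on Day -1 is a screen failure.
- SAP 3.1: none of these patients is dosed, so none is in the SS. A patient randomized on Day 0 but not dosed is also outside it.
- SAP 4.2: for non-randomized patients only the violated criteria are listed; no AE summary is planned for them.

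An event in a never-dosed patient therefore adds nothing to any safety table. The all-fatal-AE row shows the effect most plainly: a patient who dies before dosing cannot appear in it.

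**2. How far the rate could fall (illustration only).** The documents give neither the number screened nor a washout event rate. Assume 165 patients are dosed (the planned number randomized), a share p of those entering washout has an event, a share q of those is not dosed because of it, and there is no other loss in washout. Then:

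- number entering washout W = 165 / (1 − pq)
- patients with an event = Wp
- patients with an event in the SS table = Wp(1 − q)
- rate in the SS = Wp(1 − q) / 165

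| p | q | W | With event | In SS table | SS rate |
|---|---|---|---|---|---|
| 5% | 25% | 167.1 | 8.4 | 6.3 | 3.8% |
| 5% | 50% | 169.2 | 8.5 | 4.2 | 2.6% |
| 5% | 75% | 171.4 | 8.6 | 2.1 | 1.3% |
| 5% | 100% | 173.7 | 8.7 | 0 | 0% |

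Over p = 2% to 10% and q = 25% to 100%, Wpq runs from 0.8 to 18.3 patients with an event missing from the table. The direction is downward whenever affected patients are less likely to be dosed; the size depends wholly on p and q.

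**3. The arm comparison on the SAP's own scale.** Take hypothetical counts of 6 and 2 patients with treatment-emergent SAEs per 55, then add 2 further patients with pre-treatment SAEs to each arm. Agresti-Caffo adds one event and one non-event per arm.

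- Treatment-emergent only: 7/57 − 3/57 = 7.0 points. SE = √(0.1228 × 0.8772/57 + 0.0526 × 0.9474/57) = 0.0526; half-width 1.96 × 0.0526 = 10.3 points.
- With pre-treatment events: 9/57 − 5/57 = 7.0 points. SE = √(0.1579 × 0.8421/57 + 0.0877 × 0.9123/57) = 0.0611; half-width 12.0 points.

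The estimate does not move. The interval widens by 12.0/10.3 − 1, about 16%. This assumes the added events fall in patients not already counted. A patient with both kinds of event counts once; if the two were independent, with a pre-treatment share a = 2/55, the crude difference of 4/55 = 7.3 points would be multiplied by 1 − a, giving 7.3 × 53/55 = 7.0 points, a small change.

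**The case against.** The strongest reply is that little is lost. SAP 4.8.1 lists every AE in the eCRF by patient, with separate listings of SAEs and deaths, and Protocol 8.3.1.4 sends SAEs from consent onward to the sponsor within 24 hours. The treatment comparison has its own clean rows, and the tables by system organ class and preferred term are treatment-emergent only. The safety objective concerns CPL500036 given for 28 days; washout safety in undosed patients is not an endpoint. All of this stands, and it keeps the point minor. It does not supply a rate or denominator for rows the SAP itself chose to tabulate. SAP 4.1.4 also puts a randomized treatment group in every listing without saying how patients who were never randomized are shown.

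A reader might infer more than the documents support:

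- *That the pre-treatment rows are near zero by construction.* Screen failure needs a broken criterion, not merely an AE. Insomnia or headache breaks none, and worsening psychosis does not breach the PANSS and CGI-S entry criteria, which set minimum severity and exclude marked improvement. The bias chiefly concerns events that lead to exclusion.
- *That washout harm is concealed.* The listings are worded to include it.
- *That the SAE contrast between arms is diluted.* A ratio would fall in the example, from 6/2 = 3 to 8/4 = 2, but the SAP reports a difference. Frequent pre-treatment SAEs in the SS would also sit badly with the premise that most affected patients are removed.

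It is also fair to object that all consented patients is too broad a denominator for washout risk, since it includes patients who fail initial screening and unmedicated patients with no washout. The fix allows for that.

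**Conclusion.** The point holds as a minor reporting defect. The population rule makes the tabulated pre-treatment rates conditional on being dosed, so they are biased low, chiefly for events that led to exclusion. The documents do not allow the amount to be computed; the figures of 3.8% to 0% for a true 5% rest on assumed inputs. Intervals on the pre-treatment row are uninformative. In the all-AE and SAE rows, pre-treatment events add noise: about 16% more width in the example, with no shift in the expected difference apart from the small effect of patients who have both kinds of event. Rows for TEAEs and treatment-emergent SAEs, and all efficacy results, are unaffected.

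A related conflict limits what any table can show. Protocol 8.3.1.1.1 treats worsening of a pre-existing illness as an AE only in the Treatment Period, whereas SAP 4.8.1 counts worsening between consent and first dose as a pre-treatment AE. Worsening in washout may therefore not have been recorded at all.

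**What to change.** 1. In SAP 4.8 and 4.8.1, summarise pre-treatment AEs, SAEs and deaths descriptively for all consented patients, without arm comparison. Show those who entered washout separately, split into dosed and not dosed.
2. Restrict between-arm differences and 95% CIs to the treatment-emergent rows.
3. State that the AE, SAE and death listings include non-randomized patients, and how their treatment-group column is filled.
4. Reconcile Protocol 8.3.1.1.1 with SAP 4.8.1 on worsening before the first dose, and say in the report which rule governed data collection.

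The cost is SAP wording and one descriptive table from events already collected, with one or two extra denominators to define. The table cannot recover worsening that was never recorded. No efficacy or treatment-emergent analysis changes.
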